13.4. Reporting Adverse Events

The Investigator will notify the Sponsor of an adverse event by e-mail, facsimile, or telephone as soon as possible and no later than 24 hours from discovery for any serious /significant adverse events, and 2 days from discovery for any non-significant adverse event. In addition, a written report will be submitted by the Principal Investigator to the IEC/IRB according to their requirements (Section 13.4.2). The report will comment whether the adverse event was considered to be related to the test article, study treatment or study procedures.

13.4.1. Reporting Adverse Events to Sponsor

Serious/Significant Adverse Events

The Investigator will inform the sponsor of all serious/significant adverse events occurring during the study period as soon as possible by e-mail, fax, or telephone, but no later than 24 hours following discovery of the event. The Investigator is obligated to pursue and obtain information requested by the Sponsor in addition to that information reported on the eCRF. All subjects experiencing a serious/significant adverse event must be followed up and all outcomes must be reported.

When medically necessary, the Investigator may break the randomization code to determine the identity of the treatment that the subject received. The Sponsor and study monitor should be notified prior to unmasking the test articles.

In the event of a serious/significant adverse event, the Investigator must:

- Notify the Sponsor immediately
- Obtain and maintain in the subject's records all pertinent medical information and medical judgment for colleagues who assisted in the treatment and follow-up of the subject
- Provide the Sponsor with a complete case history which includes a statement as to whether the event was or was not related to the use of the test article
- Notify the IEC/IRB as required by the IEC/IRB reporting procedure according to national regulations

Unanticipated (Serious) Adverse Device Effect (UADE)

In the event of an Unanticipated (Serious) Adverse Device Effect (UADE), the Investigator will submit a report of the UADE to the Sponsor and IEC/IRB as soon as possible, but no later than 24 hours after the Investigator first learns of the effect. This report is in addition to the immediate notification mentioned above.

The Sponsor must conduct an evaluation of the UADE and must report the results of the evaluation to FDA, the IEC/IRB and participating Investigators within 10 working days after the Sponsor first receives notification of the effect.

Non-Serious Adverse Events

All non-serious adverse events, including non-serious adverse device effects, will be reported to the sponsor by the Investigator no later than 2 days from discovery.

13.4.2. Reporting Adverse Events to the Responsible IEC/IRB and Health Authorities

Adverse events that meet the IEC/IRB requirements for reporting must be reported within the IEC/IRB's written guidelines. Each clinical site will refer to and follow any guidelines set forth by their Approving IEC/IRB. Each clinical site will refer to and follow any guidelines set forth by their local governing Health Authorities.

The Sponsor will report applicable Adverse Events to the local health authorities according the written guidelines, including reporting timelines.

13.4.3. Event of Special Interest

None.

13.5. Reporting of Pregnancy

Subjects reporting pregnancy (by self-report) during the study will be discontinued after the event is recorded as an Adverse Event. Once discontinued, pregnant participants and their fetuses will not be monitored for study related purposes. At the Investigator's discretion, the study participant may be followed by the Investigator through delivery. However, this data will not be collected as part of the clinical study database. Pregnant participants are not discontinued from contact lens or solution related studies for safety concerns, but due to general concerns relating to pregnancy and contact lens use. Specifically, pregnant women are discontinued due to fluctuations in refractive error and/or visual acuity that occur secondary to systemic hormonal changes, and not due to unforeseen health risks to the mother or fetus.

14. STATISTICAL METHODS

14.1. General Considerations

All data summaries and statistical analyses will be performed using the Statistical Analysis System (SAS) software Version 9.4 (SAS Institute, Cary, NC). Throughout the analysis of data, the results for each subject/eye will be used when available for summarization and statistical analysis. Unscheduled visits will be summarized separately and will be excluded from the statistical analysis.

Summary tables (Descriptive statistics and/or frequency tables) will be provided for all baseline variables, efficacy variables and safety variables as appropriate. Continuous variables will be summarized with descriptive statistics (n, mean, standard deviation [SD], median, minimum and maximum). Frequency count and percentage of subjects or eyes within each category will be provided for categorical data.

Summaries will be presented by study lens type and will be performed separately by completion status (Safety Population or Per-Protocol Population). All analyses will be conducted on per-protocol population (see Section 14.3).

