3.3	Ocular Symptoms	Subjects will respond to a verbal open-ended symptoms questionnaire.	
3.4	Entrance Visual Acuity	
Record the distance and near Snellen visual acuity with the subjects' habitual correction in place (OD, OS, and OU) to the nearest letter. Subjects must read the smallest line until at least 50% of the letters are read incorrectly.
 
Note: Use the ETDRS 2000 Series Chart 1 or 2 near card placed at 40 cm to measure the Near visual acuity.
	
3.5	Lens Removal	Have the subject remove their habitual lenses and store in an approved storage solution.	
3.6	Biomicroscopy	
FDA Slit Lamp Classification Scale will be used to grade the findings and determine eligibility.
 
For the conjunctival redness [REDACTED] 0.5 unit increments will be used in the grading. Corneal Staining Assessment [REDACTED] will be graded in 1.0 increments.
 
If any of these slit lamp findings are Grade 3 or higher, the subject will be discontinued. If discontinued a final examination must be completed.
 
If the clearance of the fluorescein needs to be expedited, preservative-free rewetting drops or
	[REDACTED] [REDACTED] [REDACTED]

		saline may be instilled.	
3.7	Continuance	Determine whether the subject is eligible to continue in the study based on the examination findings.	

Visit 3: Treatment 2 Lens Fitting			
Step	Procedure	Details	
3.8	Lens Selection	Select the monovision power based on the lens power dispensed at Visit 1. Record the Test lens parameters (power and lot number).	
3.9	Lens Insertion	Subjects will insert the lenses themselves. If the lens is uncomfortable, inspect for damage and remove, reinsert or replace as necessary. Damaged lenses will be stored in labeled vial with sterile saline, and clearly differentiated from the other worn lenses that will be shipped back to the Sponsor. Complete the Quality Product Complaint form.	
3.10	Lens Settling	Allow the study lenses to settle for a minimum of 10 minutes.	
3.11	Determine Visual Satisfaction	Determine if the subject's vision is acceptable with the lenses. Allow the subject to look down a hallway or out of a window for distance vision assessments, and for them to read a book, magazine or similar for near vision. Note: If the subject's vision is unacceptable the subject will be discontinued. Complete the final evaluation. (No Modifications allowed)	

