3.12	Distance and Near Entrance Visual Acuity	Measure the distance and near visual acuity OD, OS and OU. Record the results. For near measures use the ETDRS 2000 Series Chart 1 or 2. The acuity will be recorded to the nearest letter OD, OS and OU.	
3.13	Distance Over-Refraction and Distance Visual Acuity	Perform a distance over-refraction OD and OS using loose lenses outside of the phoropter under ambient room illumination. The distance over-refraction may also be refined under binocular conditions. Record the results. The results of the distance over-refraction may also be checked for the impact on near vision under monocular and/or binocular conditions.	

3.14	Subjective Lens Fit Assessment	
Evaluate overall lens fit acceptance (acceptable or unacceptable) based on centration, movement and other fitting characteristics.
 
An unacceptable fit is deemed by one of the following criteria:
 
 • limbal exposure at primary gaze or with extreme eye movement; • edge lift; • excessive movement in primary and up gaze; or • insufficient movement in all three of the following conditions: primary gaze, up gaze, and Josephson push up. 
If either lens is deemed unacceptable, the subject will be discontinued from the study. Remove the lenses, perform a slit-lamp evaluation, and complete the Final Evaluation form.
	
3.15	PRO (MRD) Post-Fit Questionnaire	
The subject will evaluate the vision characteristics, comfort characteristics, handling characteristics, and visual symptoms of the study lenses using the PRO (MRD) questionnaire.
	
3.16	Distance and Near Exit Visual Acuity	
Distance and near Snellen visual acuity will be measured for each eye with the study contact lenses in place.
 
For near measures use the ETDRS 2000 Series Chart 1 or 2. The acuity will be recorded to the nearest letter OD, OS and OU.
 
Note: The distance visual acuity must be at least 20/30 OU for the lenses to be dispensed.
	
3.17	Dispensing Criteria	
The lenses will be dispensed for 12 ± 2 days.
 
 • Distance Snellen acuity equal to or better than 20/30 OU • Subject must indicate that the vision is acceptable. • Subject must indicate that the comfort of the lenses is acceptable. • Lenses must have an acceptable general lens fit. 	

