8.2. Withdrawal/Discontinuation from the Study

A subject will be withdrawn from the study for any of the following reasons:

- Subject death during the study period
- Subject withdrawal of consent
- Subject not compliant to protocol
- Subject lost to follow-up
- Subject no longer meets eligibility criteria (e.g. the subject becomes pregnant)
- Subject develops significant or serious adverse events causing discontinuation of study lens wear
- Subjects who have experienced a Corneal Infiltrative Event (CIE)
- Investigator's clinical judgment regarding the subject safety reasons (that it is in the best interest of the subject to stop treatment)
- Subject missed two consecutive study visits
- Subject not compliant with study lens wear schedule
- Subject not successfully dispensed due to lack of efficacy and safety including poor vision, poor comfort or unacceptable fit

For discontinued subjects, the Investigator will:

- Complete the current visit (scheduled or unscheduled)
- Complete the Final Evaluation, indicating the reason that the subject was discontinued from the study
- Record the spherocylindrical refraction with best corrected distance visual acuity
- Collect used test article(s) (worn or brought to the visit) from the subject and discard them, unless otherwise stated in Section 6.7.
- Collect all unused test article(s) from the subject

An additional subject may be enrolled if a subject discontinues from the study prematurely.

In cases where a subject is lost to follow-up, every possible effort must be made to contact the subject and determine the reason for discontinuation/withdrawal. The measures taken to follow up must be documented including two written attempts and a certified letter (or equivalent) as the final attempt.

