14.3. Analysis Populations

Safety Population:

All subjects who were administered any test article excluding subjects who drop out prior to administering any test article. At least one observation should be recorded.

Per-Protocol Population:

All subjects who have successfully completed all visits and did not substantially deviate from the protocol as determined by the trial cohort review committee prior to database hard lock (Per-Protocol Population). Justification of excluding subjects with protocol deviations in the Per-Protocol Population set will be documented in a memo to file.

Intent-to-Treat (ITT) Population:

All subjects regardless of actual treatment and subsequent withdrawal from study or deviation from protocol. At least one observation should be recorded.

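### All hypothesis tests use only subjects who complete every visit, although Visit 3 can remove subjects for poor vision after their Visit 2 acuity and CLUE are recorded

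*Combined protocol and SAP*

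**What the plan says.** Section 14.1 sets the population for every analysis: "All analyses will be conducted on per-protocol population (see Section 14.3". Section 14.3 defines per-protocol as "All subjects who have successfully completed all visits and did not substantially deviate from the protocol". Completion therefore runs through Visit 4.

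Section 14.1 also promises descriptive summaries, including efficacy variables, "performed separately by completion status (Safety Population or Per-Protocol Population". Section 14.3 defines an ITT population ("All subjects regardless of actual treatment and subsequent withdrawal from study or deviation from protocol"), but no analysis is assigned to it.

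Visual performance and the follow-up CLUE questionnaire are collected at Visits 2 and 4 (Section 7.1, Table 3). Hypothesis 4 is tied to Visit 2 in Sections 2.3 and 14.5. For hypotheses 1–3, Section 14.5 puts both time points in the model and does not say which one is tested.

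At Visit 3, step 3.11 of Section 7.2 deals with the subject whose "vision is unacceptable the subject will be discontinued. Complete the final evaluation. (No Modifications allowed". Step 3.16 adds: "The distance visual acuity must be at least 20/30 OU for the lenses to be dispensed". Section 8.2 lists as a withdrawal reason "Subject not successfully dispensed due to lack of efficacy and safety including poor vision, poor comfort or unacceptable fit", and then states: "An additional subject may be enrolled if a subject discontinues from the study prematurely".

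Section 14.9 rules out imputation in the main analysis. It plans multiple imputation as a sensitivity analysis only when dropout exceeds 15%, and it names no population for it.

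**The concern.** A subject who leaves at Visit 3 has already supplied valid primary-endpoint data, and for hypothesis 4 that is all the data the hypothesis needs. The plan discards it because of a later event, and that event can be a judgement on vision, which is what the primary endpoints measure. 20/30 corresponds to log10(30/20) = 0.18 logMAR, so a subject refused lenses at step 3.16 is, at that visit, on the failing side of either distance threshold printed in the document (+0.01 in Section 2.3, +0.10 in Section 14.5). A link with the Visit 2 scores is plausible, though not proven.

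In a randomised comparison such selection might act on both arms. Here the lens is judged against fixed historical values (Section 4.2). If the subjects removed have worse Visit 2 scores on average, leaving them out raises mean CLUE and lowers mean logMAR, and both shifts favour success. Replacement restores the sample size but not the lost scores. For the secondary hypothesis (Visit 4 minus Visit 2) the direction is not determined.

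**Working it through.** **1. The plan's own figures.** Section 14.2 reproduces as a one-sample t-test, two-sided alpha 0.05, with thresholds 0.10 (distance), 0.17 (intermediate and near) and 32 (CLUE). All nine rows match. For example, CLUE 38 against 32 with SD 17 gives n = 87 and power 0.902; near 0.12 against 0.17 with SD 0.12 gives n = 63 and power 0.902. The nominal chance of false success per hypothesis is therefore 2.5%. (The distance rows match +0.10, not the +0.01 of Section 2.3. Those sections need reconciling, but this point does not depend on it.)

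**2. Inputs.** From Section 14.2: 80 completers, SD 17 for CLUE and 0.12 for logMAR. Assumed, because the documents give no values: the fraction f removed for vision-linked reasons, and the correlation r between the Visit 2 score and staying in.

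**3. Bias.** Remove the lowest fraction f on a latent normal scale that has correlation r with the score (scored so that higher is better). The completers' mean shifts by

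bias = r × SD × φ(z_f) / (1 − f).

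For f = 5%, z_f = −1.645 and φ = 0.1031. With r = 0.5:
- shift = 0.5 × 0.1031 / 0.95 = 0.0543 SD
- CLUE: 0.0543 × 17 = 0.92 points
- logMAR: 0.0543 × 0.12 = 0.0065

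Approximate false success is 1 − Φ(1.96 − 0.0543 × √80) = 1 − Φ(1.474) = 7.0%. Simulation gives 6.9%.

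**4. Range.** The true mean is set at the threshold, removed subjects are replaced until 80 complete, and each setting has 40,000 simulated one-sample t-tests. Subjects removed = 80/(1 − f) − 80. Each range runs from r = 0.3 to r = 0.5.

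| f | Removed | CLUE bias | logMAR bias | False success |
|---|---|---|---|---|
| 1.25% | 1.0 | 0.17–0.28 | 0.0012–0.0020 | 2.9–3.6% |
| 2.5% | 2.1 | 0.31–0.51 | 0.0022–0.0036 | 3.4–4.4% |
| 5% | 4.2 | 0.55–0.92 | 0.0039–0.0065 | 4.6–6.9% |
| 10% | 8.9 | 0.99–1.66 | 0.0070–0.0117 | 7.7–14.4% |
| 15% | 14.1 | 1.40–2.33 | 0.0099–0.0165 | 11.0–24.4% |

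At r = 0 the rate is 2.4–2.7% for every f. If every subject with Visit 2 data is analysed, it also stays at about 2.5%, whatever r is.

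**5. Scale.** Planned gaps to threshold are 6–10 CLUE points (38–42 against 32) and 0.05–0.09 logMAR for intermediate and near (0.08–0.12 against 0.17). The bias is small beside these, so it matters mainly when true performance lies near a threshold.

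**6. All four together.** With all four true means at threshold and an assumed correlation between endpoints of 0.3–0.6, the chance of falsely passing all four is 0.2–2.4% at f = 10%. This is not the worst case: if three endpoints pass comfortably, the per-hypothesis rate applies.

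**The case against.** **Removal may be rare.** Visit 3 repeats a lens power that the subject accepted at Visit 1 after up to two modifications, with 20/30 or better, and all subjects are adapted monovision wearers. Exits for comfort, fit, slit-lamp findings or non-compliance need not track vision. This stands: nothing in the documents supports a vision-linked loss of 10–15%, and those rows are illustrative. With one to four subjects removed, false success is 2.9–6.9% and CLUE bias is at most 0.92 points, against a standard error of 17/√80 = 1.9.

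**The selection would be visible.** Efficacy summaries are promised for the Safety Population, which keeps these subjects. If they are tabulated by visit, a reader could compare the two Visit 2 means. That is fair, but it is description. The success decision still rests on completers.

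**Section 14.9 covers dropouts.** Its natural purpose is to bring them in. Read literally with Section 14.1, however, it runs on a set that contains none, and it is not required at or below 15% dropout. The section's remark that past trials do not show systematic dropout comes without figures, while this protocol itself prescribes removal for vision.

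**The simulation is simple.** It omits the covariates, the mixed model and the truncation by the Visit 1 acuity requirement. The direction does not depend on these; the exact size does.

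**A wider set admits substantial deviators.** True. Keeping per-protocol as a supportive analysis shows what they contribute.

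**Conclusion.** The concern holds and should be fixed. The text is clear: recorded Visit 2 endpoint data are excluded from every test because of a later event that can be poor vision itself. In a single-arm threshold test, any positive link between score and staying in moves the result toward success; with no link there is no bias. Confidence is high on the text and the direction. The size rests on the assumed removal rate and correlation: close to nominal for one subject removed (2.9–3.6%), up to nearly three times nominal at 5% (6.9/2.5 = 2.8), and nearly six times at 10% with correlation 0.5 (14.4/2.5 = 5.8). None of these rates would trigger the planned sensitivity analysis, so the plan as written contains no tested estimate that would show which case applies.

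**What to change.** - **Section 14.1:** run the primary tests of hypotheses 1–4 on all dispensed subjects with at least one observed post-dispensing endpoint value, using every observed Visit 2 record and any Visit 4 record in the planned mixed models. Keep per-protocol as supportive.
- **Section 14.3:** define this set explicitly. The ITT definition as worded sets no dispensing condition and accepts any observation.
- **Section 14.5:** state the time point at which hypotheses 1–3 are tested.
- **Section 14.9:** name all dispensed subjects as the multiple-imputation population and drop the 15% trigger, so that subjects lost before Visit 2 are addressed. Imputation will not by itself cure loss that depends on unobserved scores.
- **Reporting:** give the number not dispensed at Visit 1, who remain outside this set.

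The first two changes carry the correction; the others are secondary. The cost is SAP wording and a few extra model runs on data already collected, with no new visits or subjects. The estimate may come out slightly less favourable.

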14.2. Sample Size Justification

A total of 80 subjects (48 myopes and 32 hyperopes) are targeted to complete the study.

Using the POWER procedure in SAS 9.4, below is the summary of sample size required based on the different assumptions of the true LogMAR visual acuity and CLUE scores. The sample size was calculated for the non-inferiority tests (using 0.05 as the margin) with at least 90% of statistical power and 2-sided type I error of 0.05. Assuming the true LogMAR visual acuity is between 0.00 to 0.05 (distance) or 0.08 to 0.12 (near), and true CLUE vision score is between 38 to 42 points.

- Binocular LogMAR visual acuity (distance)

True Value	Estimated Standard Deviation	# of subjects needed	Actual Power
0.00	0.12	18	0.915
0.02	0.12	26	0.904
0.05	0.12	63	0.902

- Binocular LogMAR visual acuity (intermediate and near)

True Value	Estimated Standard Deviation	# of subjects needed	Actual Power
0.08	0.12	21	0.905
0.10	0.12	33	0.901
0.12	0.12	63	0.902

- CLUE vision score

True Value	Estimated Standard Deviation	# of subjects needed	Actual Power
38	17	87	0.902
40	17	50	0.903
42	17	33	0.906

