4.2. Study Design Rationale

The study is intended to evaluate the initial performance, of a photochromic lens fit as monovision, in terms of the subjective response and visual acuity, after a period of lens dispensing. The single-ARM study is used as the performance will be measured against historical performance measures used in previous multifocal contact lens studies. A washout period and lens re-dispensing was used to evaluate the reproducibility and repeatability of the subjective vision response.

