8. SUBJECTS COMPLETION/WITHDRAWAL

8.1. Completion Criteria

Subjects are considered to have completed the study if they:

- provided informed consent
- they are eligible
- completed all study visits

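### Section 14.2 states at least 90% power for a true CLUE score of 38 to 42, but 80 subjects give 87.7% at 38, and its 0.05 non-inferiority margin does not match the superiority criteria of Section 14.5

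*Combined protocol and SAP*

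**What the plan says.** On sample size, Section 14.2 states: "A total of 80 subjects (48 myopes and 32 hyperopes) are targeted to complete the study". On the type of test it says: "The sample size was calculated for the non-inferiority tests (using 0.05 as the margin"). Power and alpha are set in the same sentence: "with at least 90% of statistical power and 2-sided type I error of 0.05". The assumed ranges of true values are 0.00 to 0.05 logMAR at distance, 0.08 to 0.12 logMAR at near, and for CLUE a "true CLUE vision score is between 38 to 42 points". Three small tables follow, giving the subjects needed at three true values for each endpoint. The CLUE table (SD 17) lists 87 at a true score of 38, 50 at 40 and 33 at 42. Nothing in the section links the target of 80 to a particular row.

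On who is analysed, Section 14.1 says: "All analyses will be conducted on per-protocol population (see Section 14.3"). Section 14.3 defines that population as: "All subjects who have successfully completed all visits and did not substantially deviate from the protocol as determined by the trial cohort review committee". Section 8.1 counts as completers those who consented, were eligible and "completed all study visits".

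On the tests, Section 14.5 concludes superiority when the upper 95% confidence limit lies below +0.10 logMAR at distance and below +0.17 at intermediate and near, and when the lower limit for CLUE exceeds 32. It mentions neither non-inferiority nor a margin. Section 2.3 agrees on +0.17 and 32 but gives +0.01 logMAR for distance. Section 4.2 says of the single-arm design that "the performance will be measured against historical performance measures used in previous multifocal contact lens studies".

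**The concern.** There are two linked problems.

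- **Power.** The target of 80 is below the 87 that the section's own table requires at the lower end of its assumed CLUE range, yet the text gives 90% as a minimum without qualification. CLUE is one of four primary hypotheses that must all be met before the secondary hypothesis is tested, so its power should be stated accurately. The target also counts completers, while the analysis set can be smaller.
- **Description of the tests.** Section 14.2 names non-inferiority with a 0.05 margin; Section 14.5 specifies superiority to fixed limits. One margin is quoted for endpoints on two scales, logMAR and CLUE points. A reader of Section 14.2 cannot tell which comparison was powered.

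**Working it through.** **Inputs.** From Section 14.2: SD 0.12 (logMAR) and 17 (CLUE), two-sided alpha 0.05, the nine true values, target n = 80. From Section 14.5: limits L = 0.10 (distance), 0.17 (intermediate and near) and 32 (CLUE).

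**Formula.** One-sample t-test. With d = |true value − L|, the noncentrality is δ = (d/SD)·√n on n − 1 degrees of freedom. Power = P(|T| > t₀.₉₇₅,ₙ₋₁), where T is noncentral t with parameter δ.

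**Step 1: reproduce the plan's tables, then set n = 80.**

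| Endpoint, true value | d | Printed n (power) | Recomputed n (power) | Power at n = 80 |
|---|---|---|---|---|
| Distance 0.00 | 0.10 | 18 (0.915) | 18 (0.915) | >0.999 |
| Distance 0.02 | 0.08 | 26 (0.904) | 26 (0.904) | >0.999 |
| Distance 0.05 | 0.05 | 63 (0.902) | 63 (0.902) | 0.957 |
| Near 0.08 | 0.09 | 21 (0.905) | 21 (0.905) | >0.999 |
| Near 0.10 | 0.07 | 33 (0.901) | 33 (0.901) | 0.999 |
| Near 0.12 | 0.05 | 63 (0.902) | 63 (0.902) | 0.957 |
| CLUE 38 | 6 | 87 (0.902) | 87 (0.902) | **0.877** |
| CLUE 40 | 8 | 50 (0.903) | 50 (0.903) | 0.986 |
| CLUE 42 | 10 | 33 (0.906) | 33 (0.906) | 0.999 |

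All nine rows reproduce. Each reaches 90% at its own n.

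**Step 2: CLUE at 38 in detail.** At n = 80, δ = (6/17)·√80 = 3.157 and the critical value is 1.990, giving power 0.877 (0.884 by normal approximation). At n = 86 power is 0.899; at n = 87, δ = 3.292 and power is 0.902. So 80 is 7 subjects short, and the gap is 90.0 − 87.7 = 2.3 percentage points. With n fixed at 80, power reaches 90% at a true score of 38.24.

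**Step 3: fewer than 80 analysed.** The documents give no rate of per-protocol exclusion, so 76 and 72 (5% and 10% loss) are assumptions.

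| Analysed | CLUE 38 | Weakest acuity rows (0.05 distance, 0.12 near) | CLUE 40 |
|---|---|---|---|
| 80 | 87.7% | 95.7% | 98.6% |
| 76 | 85.9% | 94.8% | 98.2% |
| 72 | 84.0% | 93.7% | 97.6% |

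The eight scenarios other than CLUE at 38 stay at or above 90% down to 63 analysed.

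**Step 4: does the 0.05 margin enter the calculation?**

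- Adding 0.05 to the acuity limits gives 0.15 and 0.22. The required n would be 9, 12 and 18 (distance) and 10, 13 and 18 (near), against the printed 18, 26, 63 and 21, 33, 63.
- Moving the CLUE limit by 0.05, to 31.95, would require 85, 49 and 33, against the printed 87, 50 and 33.

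The tables therefore use the Section 14.5 limits with nothing added. The 0.05 could already be inside the acuity limits (0.05 + 0.05 = 0.10; 0.12 + 0.05 = 0.17), but no section says so.

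**Step 5: which distance limit was used?** Lower logMAR is better. Against +0.01, true values of 0.02 and 0.05 lie on the failing side, so no sample size gives power there. The distance rows fit only +0.10.

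**The case against.** The strongest reply is that the tables list scenarios, the 90% applies to each row at its own n, and no sentence promises 90% in every row with 80 subjects. The 87 is printed openly, and no tabulated number is wrong. That is fair as a reading of the tables. But the same paragraph gives 90% as a minimum together with an assumed range that includes 38, and does not say that the target falls short at that end.

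Second, the gap is small: one scenario of nine, and 0.24 of a 4-point range. This stands, and is why only wording is at issue.

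Third, 87.7% is a t-test figure, while Section 14.5 plans a mixed model with baseline adjustment and two time points. If 17 is an unadjusted SD, a residual SD of about 16.35 (an assumed baseline correlation of about 0.27) would restore 90% at n = 80. Random site effects could act in the other direction. The documents give no correlation or site variance, so the net effect is unknown, and the plan's own figures are t-test figures.

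Fourth, Sections 5.2 and 8.2 allow discontinued subjects to be replaced, and Section 8.2 withdraws the non-compliant, so some deviators would be replaced before completing. This weakens the per-protocol point but does not remove it: replacement does not cover completers excluded at cohort review.

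Fifth, non-inferiority to a reference plus a margin is algebraically superiority to the resulting limit, so for acuity the difference may be one of naming. That also stands as a possibility, but it is unexplained and does not extend to CLUE.

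**Conclusion.** The point holds, at modest size. By the plan's own method and inputs, 80 analysed subjects give 87.7% power for CLUE at a true score of 38, against a stated minimum of 90%. The other eight scenarios have at least 95.7%. This assumes SD 17, limit 32, two-sided 0.05, a one-sample t-test and no per-protocol exclusions; exclusions would widen the gap, and the mixed model could move it either way. The 0.05 non-inferiority wording does not describe the superiority criteria of Section 14.5, is not added to any limit in the tables, and has no evident meaning for CLUE. The tables also show that the distance calculation used +0.10, which conflicts with the +0.01 in Section 2.3. The target of 80 is defensible; its description needs correcting.

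**What to change.** Wording changes only, in this order:

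1. Reconcile the distance limit between Section 2.3 (+0.01) and Section 14.5 (+0.10), noting that the sample size table fits only +0.10.
2. Restate the power in Section 14.2, for example: *80 analysed (per-protocol) subjects give 87.7% power for CLUE at a true score of 38 and at least 95.7% in the other tabulated scenarios, by one-sample t-test at two-sided 0.05. Per-protocol exclusions would lower this (for example to 85.9% for CLUE at 38 and 94.8% for the weakest visual acuity scenarios with 76 analysed), and power under the planned mixed model may differ.*
3. Describe the tests as superiority comparisons with the Section 14.5 limits. Delete the 0.05 margin, or explain how it enters the visual acuity limits and state that it does not apply to CLUE.

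Optional additions, not corrections of errors: the joint power for the four primary hypotheses, and whether the SD of 17 is before or after baseline adjustment.

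The cost is a few sentences and no extra recruitment. The stated CLUE power at 38 becomes 2.3 percentage points less favourable.
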